Testing for the presence of mediation (illustrated in Figure 1) will allow us to determine the extent to which pain catastrophizing^{28,29,39} mediates the relationship between pain coping skills training and outcome. The dashed

line between pain coping skills training and WOMAC Pain represents the hypothesized mediation (either partial or complete) of pain coping effects by pain catastrophizing. Understanding whether catastrophizing is a mediator for pain coping skills treatment response will provide a causative explanation for how pain coping skills training effectively improves outcomes following knee arthroplasty. If our study finds that pain coping skills training (CST) is effective and that pain catastrophizing explains these effects, the field of orthopaedic surgery could experience substantive changes in the way in which patients with knee arthroplasty are treated; to the benefit of many patients. Surgeons may begin to routinely screen for high pain catastrophizing and initiate pain

coping skills training for selected patients.

Innovation: Specific Aim 1

Current clinical paradigms do not discuss formal identification of patients at-risk for poor outcome due to poor pain coping.⁴⁰ Nor do these paradigms address the use of perioperative interventions to reduce poor outcome risk. The current application challenges this practice paradigm. If our trial is successful, as we anticipate it will be based on our pilot work, the research will provide strong evidence to reconsider this traditional approach and may improve outcomes for thousands of patients who currently are at-risk for poor outcome.

Previous work by our group²⁹ and others^{27,28,31,39} has identified a TKA patient subgroup at high risk for poor outcome. Patients with high levels of pain catastrophizing have been consistently shown to have a higher rate of persistent pain and compromised function compared to non-catastrophizers. Our study is innovative because it is the first trial, to our knowledge, to target a specific surgical subgroup of patients at risk for poor outcome. In addition, we completed a search of ClinicalTrials.gov and the World Health Organization registry portal on June 1, 2011 and found no trials examining the impact of pain coping skills behavioral interventions for patients with knee arthroplasty.

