Although it is possible that depressive symptoms could interfere with treatment efficacy, it is also possible that those with depressive symptoms might benefit more from the treatment than those who are not depressed, given that the intervention teaches skills that can help in the treatment of depression. By excluding only the participants with severe depressive symptoms, and including patients with other levels of depressive symptoms, generalizability will be enhanced and we will be able to determine if the intervention is more or less effective among persons with depressive symptoms, relative to non-depressed persons. In our pilot study of 112 knee arthroplasty patients with high pain catastrophizing as defined in our trial, a total of 3 patients (2.7%) had PHQ scores of 20 or higher. Depressive symptoms will be examined as a potential moderator of treatment effect in the analysis.

Other exclusion criteria were selected to reduce the risk of confounding in the trial. For example, patients receiving revision surgery have poorer outcomes as compared to patients undergoing primary knee arthroplasty.⁵⁶ Screening will be conducted via telephone by study staff after the patient has consented for surgery.

Randomization and Blinding

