We recruited a consecutive series of 10 patients 1 year following knee arthroplasty to determine if the SPPB and the six minute walk test would be well tolerated. In addition, we were concerned about possible ceiling effects on the SPPB which can occur with high functioning elderly persons.¹⁰² SPPB total scores range from 0 to 12. The mean score on the SPPB summary scale for the patients was 8.5 (sd = 2.3) and ranged from 3 to 11. We concluded that the SPPB and the 6-minute walk test are well tolerated by patients receiving knee arthroplasty and that some individual tests comprising the SPPB will likely demonstrate ceiling effects. We will therefore use the composite SPPB score and a time-based calculation of the composite SPPB score¹⁰³ in addition to the 6-minute walk test.

Primary and Secondary Outcome Measures and Endpoints

Participants from all three arms will be evaluated by an assessor who is blinded to group allocation at baseline, 1 week prior, and 1 week after, 2 months, 6 months and 1 year after surgery. The baseline assessment will include age, gender, comorbidity^{14,104}, education and occupation, current medications, mental healthcare received and a variety of pain and psychological characteristics including depression, anxiety, pain coping etc. Follow-up outcomes will include measures of pain, function, catastrophizing and depression. (see MOOP in appendix for a complete description).

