moderators for patients with knee arthroplasty who may particularly benefit from pain coping skills training are the following: expectations prior to surgery¹³⁵⁻¹³⁷, self efficacy^{138,139}, extent of social support^{9,140} and depression.²⁷ Recent evidence suggests that psychological states of depression, low expectations for recovery from surgery, poor self-efficacy and reduced social support increase risk of poor outcome following surgery, and may therefore modify the effects of pain coping skills training. Because our study is not powered to test for these potential moderators, they will be assessed only for the primary outcome of WOMAC Pain at 1 year. This analysis will be performed by including a three-way Moderator X Treatment group X Time interaction term in the mixed models analyses. It is our intent to assess whether these variables independently predict those patients who are more likely to respond to pain coping skills training versus arthritis education or usual care. Pain coping skills training emphasizes pain coping strategies, unlike usual care or arthritis education and because of this emphasis, we suspected that coping strategies training would be particularly effective in patients with less healthy psychosocial features. Knowing whether any of these potential moderators actually predict response to treatment will aid in better identifying individuals who are more likely to respond to the intervention.

Cost Analysis

We will conduct a cost analysis to compare mean total costs incurred over the one year follow-up period in the KASTpain study between patients randomized to coping skills training vs. arthritis care (and vs. usual care). We will compare each component (medical costs and indirect costs) and estimate intervention costs. All three components will comprise total costs which will also be compared. Total costs, from the societal perspective, will consist of direct medical costs, intervention-related costs and indirect costs. From the health care system (or payer) perspective, indirect costs will be excluded. Sensitivity analyses will be performed to evaluate the impact of scaling up the intervention (i.e. more patients per session; fixed costs allocated over more patients) and methodological choices for cost assignment.^{141,142}

Cost-Effectiveness Analysis

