Periodic and ad-hoc reporting will be utilized to show subject recruitment and retention data stratified by site. Automated email agents will electronically notify site staff and investigators of upcoming and overdue subject follow-ups. Upon request, the data manger will provide de-identified data in a form agreeable to the biostatistician. In addition, the DMG will provide timely troubleshooting assistance via phone and email and answer inquiries from research staff and investigators. The investigators will develop a User’s Guide to aid the study staff with data management tasks should the study be funded.

Approach: Specific Aim 2

We will collect Pain Catastrophizing Scale, WOMAC Pain and Disability Scale and a verbal pain rating scale scores on all patients at six time points (4 to 6 weeks prior to surgery, 1 week prior to surgery, 1 week following surgery, 2 and 6 months following surgery and 1 year following surgery). Our rationale is that we want to capture the short- and intermediate-term temporal progression of changes in catastrophizing prior to and following treatment to describe changes in mediation over time. The primary outcome measure will be the WOMAC Pain scale, collected at all assessment points. The independent variable will be treatment condition (Pain Coping Skills Training vs Arthritis Education vs usual care). (Figure 1)

Our hypothesis is that the effects on WOMAC Pain by the pain coping skills arm will be either partially or fully mediated by pain catastrophizing, whereas effects by arthritis education or usual care will either not be mediated by pain catastrophizing or mediated to a significantly lesser extent as compared to the pain coping skills arm. Mediation will be investigated using the three-step approach described by Baron and Kenny¹⁷ and modified for randomized trials by Smeets and colleagues.¹⁴⁴ A series of 3 multilevel regression analyses will be used to determine if pain catastrophizing mediates the effect of the interventions on pain as measured with the WOMAC Pain scale at the various time points. WOMAC Disability and verbal pain rating scores will serve as secondary outcome measures for the mediation analysis.

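### Aim 2 promises a causal explanation, but the catastrophizing-to-pain step is not randomised and the mediation plan states no covariates, confounding assumption or sensitivity analysis for it

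*Combined protocol and SAP*

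**What the plan says.** Significance: Specific Aim 2 states that knowing whether catastrophizing mediates the response "will provide a causative explanation for how pain coping skills training effectively improves outcomes following knee arthroplasty". It adds that, if training works and catastrophizing explains why, surgeons may start routine screening for it.

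Approach: Specific Aim 2 gives the method. "The independent variable will be treatment condition", with three arms. "Mediation will be investigated using the three-step approach", in a version adapted for randomised trials that is cited but not described. "A series of 3 multilevel regression analyses will be used to determine if pain catastrophizing mediates the effect of the interventions on pain". PCS and WOMAC Pain are both collected at six time points because "we want to capture the short- and intermediate-term temporal progression of changes in catastrophizing". Catastrophizing is the only mediator named.

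Depression appears in other sections:
- **Participants:** the eligibility rationale says "the intervention teaches skills that can help in the treatment of depression" and then assigns depressive symptoms the role of a potential moderator.
- **Data Analysis:** depression is one of four psychosocial factors said to "increase risk of poor outcome following surgery", again as a reason to study moderation.
- **Primary and Secondary Outcome Measures and Endpoints:** "Follow-up outcomes will include measures of pain, function, catastrophizing and depression".

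**The concern.** Randomisation makes the arms comparable. It does not make patients whose catastrophizing falls comparable with patients whose catastrophizing does not. The step from catastrophizing to pain is therefore observational, and a causal reading needs an explicit assumption that nothing unmeasured drives both. The plan makes the causal claim without stating that assumption, without naming anything to adjust for, and without a check on how far the result depends on it.

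At stake is Hypothesis 4. It could be declared partly or fully supported even if changing catastrophizing did nothing to pain, and that result would then feed the screening argument.

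**Working it through.** **1. What randomisation covers.** The three-step approach uses three relations.

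| Relation | Protected by randomisation? |
|---|---|
| Treatment to PCS | Yes |
| Treatment to WOMAC Pain | Yes |
| PCS to WOMAC Pain, given treatment | No |

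**2. The plan's own figure.** No figure is given for the mediation analysis. The nearest is the 91% power in Sample Size Estimations (107 per arm, difference 2.0, SD 4.34, two-sided 0.05). Check: 2.0/4.34 = 0.461; 0.461 × √(107/2) = 3.37; 3.37 − 1.96 = 1.41; power 92.1% (91.9% with the t distribution). It reproduces within about one point. It concerns the primary comparison and serves here only to supply the scale.

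**3. Spurious indirect effect.** Suppose PCS has no effect on pain. Let treatment lower PCS by *a* SD, and let PCS and pain have a within-arm residual correlation *r* from shared causes. Regressing pain on treatment and PCS then gives a PCS coefficient of *r* in SD units, so the apparent indirect effect is *a* × *r* × 4.34 points. The true value is zero.

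| *a* (SD) | Basis | *r* = 0.1 | *r* = 0.4 |
|---|---|---|---|
| 0.30 | assumed | 0.13 | 0.52 |
| 0.46 | design effect size for pain, borrowed for PCS | 0.20 | 0.80 |
| 0.71 | low end of pilot range | 0.31 | 1.23 |
| 0.96 | high end of pilot range | 0.42 | 1.67 |

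The pilot range (Pilot Intervention Study) covers disability, pain and catastrophizing together. No separate PCS value is given, so using it for PCS is itself an assumption. The values of *r* have no source in the documents.

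**4. How often mediation would be declared.** The three regressions were simulated at one time point: two arms of 107, total effect 0.46 SD, true mediated share zero, each step tested at two-sided 0.05, 4,000 runs per setting.

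| *a* | *r* = 0 | *r* = 0.1 | *r* = 0.2 | *r* = 0.3 |
|---|---|---|---|---|
| 0.30 | 3% | 17% | 46% | 55% |
| 0.46 | 4% | 26% | 71% | 85% |
| 0.74 | 5% | 28% | 78% | 92% |

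For *a* = 0.46, the share of the total effect wrongly credited to catastrophizing is 10%, 20% and 30% at *r* = 0.1, 0.2 and 0.3. The planned models are multilevel and use repeated visits, so this is a simplification.

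**5. Depression as a candidate.** The Participants remark (training can help depression), the Data Analysis remark (depression raises risk) and its follow-up measurement, taken together, describe a variable that could link treatment to pain outside catastrophizing. Suppose depression were the only omitted cause, with assumed treatment effects of 0.46 SD on both PCS and depression, a PCS-depression residual correlation of 0.3 to 0.7, and a depression effect on pain of 0.3 to 0.5. Mediation by catastrophizing is then falsely declared in 21% to 85% of simulated trials. With follow-up depression in the outcome model the rate is 4.0% to 4.7%.

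**The case against.** Several points on the other side carry weight.

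- **Depression as a named pathway.** A reader might infer that the plan itself identifies depression as a second route by which treatment works and then ignores it. The documents do not support that. Both remarks are made in arguing for moderation, the Participants passage is hedged, and neither says that training relieves pain through mood. The route appears only when separate statements are joined.
- **Evidence against depression as the leading rival.** Preliminary Studies reports a cohort that measured depression, anxiety, self-efficacy and fear of movement as well as catastrophizing. After adjustment, catastrophizing was the only consistently strong psychological predictor of poor pain outcome. This stands, and gives some reason for a single-mediator model. It shows prediction, however, not that lowering catastrophizing lowers pain.
- **Size.** A reader might take the pilot rows in step 3 as showing a bias of 15% to 83% of the 2-point design effect (0.31/2.0 to 1.67/2.0). That sets an undiscounted, non-randomised two-month pilot range against a deliberately discounted target. Discounting PCS in the same proportion (0.46/0.74, also an assumption) gives 0.44 to 0.60 SD, 0.19 to 1.04 points, or 10% to 52%. Neither range is a measured defect of this trial.
- **Details elsewhere.** The cited adaptation for randomised trials may deal with covariates, and Data Analysis mentions baseline covariates for the primary model. Approach: Specific Aim 2 neither describes the one nor carries over the other.
- **Repeated assessments.** Six visits could establish temporal order if catastrophizing were lagged before pain. No lag is stated, and lagging would not remove a shared cause.
- **Consequence.** The screening remark is conditional and cautious. Efficacy in patients selected for high PCS would support it in part whatever the mechanism.

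None of this answers the central point: the causal claim goes further than the stated method.

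**Conclusion.** The point holds in a limited form. As written, the Aim 2 analysis can show an association consistent with mediation. It cannot deliver a causal explanation, because the mediator is not randomised and the plan states no covariates, no confounding assumption and no sensitivity analysis for that step. Depression is one plausible omitted cause, not an established one.

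The size of the bias cannot be obtained from the documents. The illustrative 0.13 to 1.7 points rests on an assumed PCS effect of 0.30 to 0.96 SD, an assumed residual correlation of 0.1 to 0.4, a true PCS effect of zero and the planning SD of 4.34. With no residual correlation there is no such bias.

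This should be corrected before the mediation analysis is run. It does not touch the primary endpoint or Hypotheses 1a and 1b.

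**What to change.** 1. In Approach: Specific Aim 2, add a sensitivity analysis that reports the residual mediator-outcome correlation at which the indirect effect falls to zero. In the simple model used above, this equals the within-arm residual correlation between PCS and pain seen in the data.
2. In the same section, adjust the mediator-outcome model for baseline PCS, WOMAC Pain and depression. All three are already collected. This deals with measured baseline causes only, so item 1 is still needed.
3. In Significance: Specific Aim 2, replace the causal wording with: *evidence consistent with mediation, conditional on no unmeasured mediator-outcome confounding*.
4. A model with follow-up depression as a parallel mediator may be reported as exploratory, with the note that it assumes neither mediator causes the other. If lower catastrophizing or less pain improves mood, conditioning on follow-up depression could remove real mediation or add bias.

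The cost is a little extra analysis of data already collected and a more modest claim for Aim 2. Nothing in Aim 1 changes.

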Participants who meet study inclusion criteria and consent to participate will be stratified by orthopaedic surgeon and randomized in permuted blocks of 3, one to each study group, to ensure that patients from each participating physician and site have an equal chance of being randomized to one of the 3 groups. Given that we will have 30 orthopaedic surgeons participating in the study (see Table 5 below), this approach will control for temporal and clustering effects resulting from single surgeons having imbalances in the numbers of patients in each treatment group over time. Assignment to one of the 3 groups will be accomplished with a computer generated table of random numbers created by the biostatistician and provided to the study coordinators at each site via a secure website. After collecting baseline data, each site's study coordinator will conduct treatment allocation by use of the study web site, allowing the treating surgeon and the follow-up data collectors (site coordinators and research assistants) to be blinded. We will instruct all surgeons of the importance of avoiding study contamination by not querying patients about study interventions. Surgeons also will be asked to report if they became aware of group assignment during the study. These data will be tracked and reported at the end of the study.

All data collected at each site will be obtained by data collectors who are blinded to group allocation. This will be accomplished by assigning patients to one of the three treatment groups using a secure website and then providing patients with treatment allocation information in random number matched pre-sealed opaque envelopes. Patients will be instructed to open envelopes once they return home and they will be asked not to mention their group assignment to the data collectors. Information in the envelopes will inform patients about group assignment and will instruct patients to contact site PIs if they have any questions about the treatment to which they have been assigned. Because site PIs will not be collecting data from patients, we will optimize the likelihood of keeping data collectors blinded to group allocation during the course of study.

Interventions

Pain Coping Skills Training

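### Fixed blocks of 3 within surgeon make the third assignment of every completed block certain to anyone who knows the first two; concealed, varying block sizes would largely remove this.

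*Combined protocol and SAP*

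**What the plan says.** All of the main text is in the Randomization and Blinding section. Participants are "stratified by orthopaedic surgeon and randomized in permuted blocks of 3, one to each study group". There are "30 orthopaedic surgeons participating in the study", so there are 30 strata. The stated reason is to control temporal and clustering effects that arise when one surgeon's patients are unevenly split between arms over time.

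The list is a "computer generated table of random numbers created by the biostatistician and provided to the study coordinators at each site via a secure website". After baseline data are collected, each site's "study coordinator will conduct treatment allocation by use of the study web site". The same sentence says this arrangement lets the surgeon and the follow-up data collectors be blinded, and it counts site coordinators among those collectors. Patients receive number-matched, sealed, opaque envelopes to open at home. They are asked not to tell data collectors their arm and are told to take questions about their treatment to the site investigator, who does not collect data. Surgeons are told not to ask patients about the interventions.

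Under Coordinating Center, centers are trained to apply the randomization scheme. Under Clinical Sites, sites recruit, screen and enroll. The Participants section says that study staff screen by telephone. No section mentions varying block sizes or keeping the block size from sites.

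**The concern.** With three arms at 1:1:1, a block of 3 is the smallest possible. Once two patients of a surgeon have been assigned within a block, the third can only go to the remaining arm. Knowing just the first assignment already rules out one arm for the next two patients.

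The envelopes protect the current assignment. They do not protect earlier ones, and those are known at the site: the psychologist and the nurse educator each know whom they treat, patients know their own arm, and site investigators field treatment questions. If that knowledge reached someone who screens, consents or enrolls, that person could at times foresee the next arm for that surgeon. The eligibility window of 2 to 8 weeks before surgery leaves some room to time an enrolment, and encouragement to consent can also vary. Either could make the arms differ in ways the trial does not measure. The primary outcome is self-reported pain, so such differences would matter.

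**Working it through.** **Inputs.** Block of 3, one per arm, within surgeon; 30 surgeons (Randomization and Blinding). Enrolment 402, or 134 per arm (Sample Size Estimations). Surgeons and planned enrolment by site (Table 5): VCU 3 and 100, SIU 12 and 101, IU 7 and 100, Duke 8 and 101. The plan gives no figure for predictability. The enrolment total used here does reproduce: 321 + 64 + 17 = 402.

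**Step 1: one block.** The best guess is right with probability (largest remaining count) / (remaining places).
- Position 1: 1/3. Position 2: 1/2. Position 3: 1.
- Sum 11/6, so the mean over a completed block is 11/18 = 61.1%. One assignment in three is certain.
- Under simple randomization the guess would be right 1/3 of the time and nothing would be certain.

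**Step 2: patients per surgeon.** Overall 402/30 = 13.4. If each site's patients are spread evenly over its surgeons (an assumption): SIU 101/12 = 8.4, Duke 101/8 = 12.6, IU 100/7 = 14.3, VCU 100/3 = 33.3. The range is about 8 to 33.

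**Step 3: blocks of 3 in strata of that size.** Only completed blocks have a third place.
- 13 patients (4 blocks plus 1): certain 4/13 = 30.8%; best guess (4 × 11/6 + 1/3)/13 = 59.0%.
- 8 patients (2 blocks plus 2): certain 2/8 = 25.0%; best guess (2 × 11/6 + 1/3 + 1/2)/8 = 56.3%.
- 33 patients (11 blocks): certain 11/33 = 33.3%; best guess 61.1%.

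**Step 4: whole trial.** With the even spread, completed blocks number 33 (VCU) + 29 (SIU) + 30 (IU) + 32 (Duke) = 124, and 124/402 = 30.8%. If every block were completed, the maximum would be 402/3 = 134.

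**Step 5: alternatives.** Random block sizes were simulated (4,000 runs per case). The guesser knows all past assignments and the set of possible sizes, but not the size of any given block, and applies Bayes' rule. An exact enumeration for 8 and 13 patients agrees with the simulated values to within 0.2 percentage points.

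| Scheme | Patients per surgeon | Certain | Best guess right |
|---|---|---|---|
| Fixed 3 | 8 / 13 / 33 | 25.0 / 30.8 / 33.3% | 56.3 / 59.0 / 61.1% |
| Random 3, 6 | 8 / 13 / 33 | 5.6 / 6.8 / 8.2% | 53.1 / 55.5 / 57.4% |
| Random 3, 6, 9 | 8 / 13 / 33 | 0.8 / 2.5 / 3.4% | 50.4 / 52.7 / 54.8% |

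The main gain is in certainty. The average guess improves by only 3.5 points (59.0 − 55.5) or 6.3 points (59.0 − 52.7) at 13 patients per surgeon.

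**Step 6: pace.** Over 36 months, 13.4 patients per surgeon is one every 36/13.4 = 2.7 months; it is 36/8.4 = 4.3 months at SIU and 36/33.3 = 1.1 months at VCU. A long gap makes the order harder to track. It also means an earlier patient's treatment will often have started, since the first coping-skills session is about one month before surgery.

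**The case against.** The strongest reply is that the plan intends the people who matter not to know any arm. Web allocation is described as the means of keeping the surgeon, coordinators and assistants blinded, and the patient learns the arm only from a sealed envelope opened at home. The psychologists and nurse educators who do know arms are nowhere said to screen or consent. The 31% needs someone who knows every earlier arm, in order, for one surgeon, at a typical pace of one patient every few months. Small blocks also serve a stated purpose, balance within surgeon over time. Most of this stands, and it makes the risk conditional.

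What does not stand is that the safeguards close the route. Patients are only asked not to mention their arm. The list is "created by the biostatistician and provided to the study coordinators at each site via a secure website", and the text does not say whether the coordinator sees an arm or only an envelope number. If only a number, the risk is smaller.

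A reader might infer four stronger things, which the documents do not support:
- **That coordinators personally screen and consent.** The text says only study staff and clinical sites.
- **That assessors can deduce arms.** That presupposes they already know the arms of two other patients of the same surgeon, so that blinding has already failed.
- **That the analysis can do nothing.** The primary model includes baseline covariates and contrasts change from baseline, which addresses measured imbalance, though not selection on unmeasured factors.
- **That the balance rationale rules out any other block scheme.** Varying sizes in multiples of 3 keep most of that balance.

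**Conclusion.** The concern holds as a conditional weakness in allocation concealment. As written, every completed block ends in an assignment that is certain to anyone who knows the two before it. The ceiling is 31% of assignments certain (about 25% to 33%) and 59% guessed correctly (about 56% to 61%). The ranges rest on each site's patients being evenly spread over its surgeons, and the ceiling on full knowledge of earlier arms.

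These figures should not be read as the expected rate of foreseen assignments, nor as evidence that any bias would occur. The documents show no leak to enrolling staff, and no effect on WOMAC Pain can be estimated from them. Nor do they say outright that block size never varies; they are silent on it. Sample size and power are unaffected. This is a cheap improvement to the design, best made before enrolment because selection on unmeasured factors could not be fully corrected afterwards.

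**What to change.** Use randomly varying block sizes within surgeon (3 and 6, or 3, 6 and 9), generated and held centrally, with the sizes kept out of the protocol text and all site documents and training. State in the protocol only that block sizes vary and are concealed.

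The cost is one change to the randomization program. The plan is dated 20 July 2012 and expects the first subject by 1 October 2012, so on its own timetable there is time. The downside is slightly more imbalance within low-volume surgeons. Within an open block of size b, two arms of one surgeon can differ by at most b/3, that is 1 for a block of 3, 2 for a block of 6 and 3 for a block of 9. At about 8 patients per surgeon this may favour 3 and 6.

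In the same section, reconcile the coordinator's role as the person who conducts allocation with the listing of coordinators among blinded data collectors. Say what the web page shows (arm or envelope number only), and who at each site may know earlier assignments.
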